11.2. Anti-Phage Antibody Titer

The anti-phage antibody titer will be assessed as indicated in the Schedule of Assessments in Table 1 of the Protocol Appendix A. Immunogenicity sampling times and results will be listed for the Safety Population.

11.3. Spirometry

Spirometry assessments FEV₁, FVC, and FEF₂₅₋₇₅ will be collected locally at the clinical study site. Actual liter values will be recorded. Details regarding spirometry procedures and standards will be included in the Study Manual. Spirometry will be assessed according to the Schedule of Assessments in Table 1 of the Protocol Appendix A and Timing of Sample Collection and Procedures for the Treatment Period in Table 2 of the Protocol Appendix A. Spirometry will be collected prior to sputum induction on non-Treatment Period Visits.

Observed values and mean changes from baseline will be presented for each spirometry parameter using descriptive statistics (i.e., n, mean, standard deviation, median, minimum, and maximum) by treatment group and visit, using the Safety population. If multiple measurements are to be performed at each time

This document is confidential.

point, the highest value will be used for analysis.

A by-subject listing will be provided, including each spirometry parameter, and will be sorted by subject and visit.

A by-subject line plot will be presented by spirometry parameter and cohort. Each cohort will be on a new plot, with all subjects of the same cohort on the same plot. Any unscheduled results will also be part of this plot.

The number and percentage of subjects with PCS values will be summarized by visit/timepoint and for any time post-baseline. Potentially clinically significant values will be identified for FEV₁ (forced expiratory volume) as outlined below.

Table 13.6.1 Potentially Clinically Significant Values for Forced Expiratory Volume Decrease

Parameter	Units	Criteria for PCS Values (Observed values)	
		High	Low
Forced Expiratory Volume	%	NA	70 – 99 60 – <70 50 – <60 <50

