7.6 Change in Spirometry

Spirometry will be performed per American Thoracic Society/European Respiratory Society Standards^{28,29,30,31,32} and evaluated locally at the clinical study site. FEV₁, forced vital capacity (FVC), and forced expiratory flow between 25% and 75% of the FVC (FEF₂₅₋₇₅) will be collected. Actual liter values will be recorded. Details regarding spirometry procedures and standards will be included in the Study Manual.

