5.3. Exploratory Efficacy Endpoints

The exploratory endpoints include the following:

- Anti-Pseudomonas antibiotic sensitivity of *P. aeruginosa* isolates at specified time points during the study;
- Change in *P. aeruginosa* density from Baseline;
- Change from Baseline of in vitro sensitivity of subject *P. aeruginosa* isolates to AP-PA02 and/or individual phage components;
- Change in spirometry from Baseline;
- Change from Baseline levels of induced sputum neutrophil elastase; and
- Change in quality of life as assessed by the following questionnaires:
 - Quality of Life-Bronchiectasis Questionnaire;
 - Leicester Cough Questionnaire; and
 - Saint George's Respiratory Questionnaire.

This document is confidential.

6. Analysis Sets

Subjects who enrolled prior to the first DSMB meeting and received AP-PA02 were given a lower dose (3×10^{11} PFU/day) of AP-PA02. After the first DSMB meeting, a decision was made to increase the dosage of AP-PA02 to 6×10^{11} PFU/day (see [Section 8.5](#)). Unless noted otherwise, summary outputs by treatment groups will exclude subjects who were enrolled on the study prior to the first DSMB meeting that occurred on 01Nov2023 and received AP-PA02.

Subjects who were enrolled on the study prior to the first DSMB meeting but received placebo will be 'pooled' with the subjects who were enrolled after the first DSMB meeting as the 'pooled' placebo group within their respective cohorts.

All subjects will be included in the listings.

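### SAP 11.3 uses the highest value for every spirometry parameter, but for FEF25-75 that rule tends to favour shorter blows and biases the observed value upward

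*SAP*

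**What the plan says.** SAP 11.3 opens by naming the three parameters: "Spirometry assessments FEV₁, FVC, and FEF₂₅₋₇₅ will be collected locally at the clinical study site". It then promises the same summaries for all of them: "Observed values and mean changes from baseline will be presented for each spirometry parameter using descriptive statistics". The selection rule follows: "If multiple measurements are to be performed at each time" "point, the highest value will be used for analysis". No parameter is exempted, and nothing requires the three values to come from one blow.

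Protocol 7.6 gives the definition that matters here: "forced expiratory flow between 25% and 75% of the FVC (FEF₂₅₋₇₅) will be collected". Protocol 7.6 and 8.8 require spirometry to American Thoracic Society/European Respiratory Society (ATS/ERS) standards and leave the details to a Study Manual that is not among the documents.

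Two other places bear on the rule. SAP 7.4 has a general rule for repeated observations at a visit, which takes the earliest non-missing value; 11.3 departs from it without saying that it overrides it. SAP 5.3 lists "Change in spirometry from Baseline" as an exploratory efficacy endpoint, but SAP 9.2.3 gives no method and points to a Section 10.3 that does not exist. In practice 11.3 is the only spirometry derivation for both efficacy and safety.

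**The concern.** A maximum is a sensible summary when a larger reading can only mean a better effort. That is so for FEV1 and FVC. FEF25-75 differs because its volume limits are set by the blow itself. If exhalation stops early, the recorded FVC is smaller, the 25-75% segment shifts to the earlier and faster part of the blow, and the mean flow over it goes up. A highest-value rule then leans towards the less complete blows, while the FVC in the next row of the table comes from the fullest one.

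At stake is a descriptive parameter that appears as an exploratory efficacy measure, a safety summary and a baseline characteristic (SAP 8.2). The observed level would be too high. The change from baseline could also be distorted if completeness differs between visits. Protocol 1.3.2.2 names bronchial irritation as a possible risk, and in Protocol Table 2 at least two of the five treatment-period spirometry time points fall after a dose, so such a difference is conceivable.

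**Working it through.** The documents state no figure on this point, so there is none to reproduce. Only the definition of FEF25-75 and the selection rule come from them. The emptying model, number of blows, completeness and effort variation are assumptions.

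**1. One shortened blow.** Let V(t) = FVC(1 − e^(−kt)), stopped at a fraction f of full FVC. The blow's own FVC is f·FVC, so t25 = −ln(1 − 0.25f)/k and t75 = −ln(1 − 0.75f)/k. Then

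FEF(f) = 0.5·f·FVC/(t75 − t25) = 0.5·f·k·FVC / ln[(1 − 0.25f)/(1 − 0.75f)].

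At f = 1 the logarithm is ln 3, so FEF(f)/FEF(1) = f·ln 3 / ln[(1 − 0.25f)/(1 − 0.75f)].

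| f | f·ln 3 | Denominator | Ratio |
|---|---|---|---|
| 0.98 | 1.0766 | ln(0.755/0.265) = 1.0470 | 1.028 |
| 0.95 | 1.0437 | ln(0.7625/0.2875) = 0.9754 | 1.070 |
| 0.90 | 0.9888 | ln(0.775/0.325) = 0.8690 | 1.138 |
| 0.80 | 0.8789 | ln(0.80/0.40) = 0.6931 | 1.268 |

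An assumed two-compartment obstructed lung (half the volume with time constant 0.4 s, half with 2.5 s) gives larger errors: +6.3%, +16.1% and +33.4% at f = 0.98, 0.95 and 0.90.

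**2. Choosing among three blows.** Simulation of 200,000 sets, mono-exponential emptying, f uniform from a lower limit to 1, and blow-to-blow effort CV of 0 or 5% acting on flow and volume together. Overstatement is relative to a full blow.

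| Lower limit of f | Effort CV | Highest FEF25-75 | FEF25-75 from largest-FVC blow | Shortest blow picked by highest-value rule |
|---|---|---|---|---|
| 0.90 | 0 | +10.4% | +3.5% | 100% |
| 0.90 | 5% | +12.8% | +9.2% | 59% |
| 0.95 | 0 | +5.3% | +1.8% | 100% |
| 0.95 | 5% | +8.4% | +7.4% | 48% |
| 0.98 | 0 | +2.1% | +0.7% | 100% |
| 0.98 | 5% | +5.9% | +5.8% | 39% |

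Chance alone would pick the shortest of three 33% of the time. Over effort CVs of 2-10% the range is 36-78%. At a CV of 5%, part of the overstatement in both value columns comes from selecting on variable effort, not from truncation.

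I reran the 0.90, CV 5% row taking FEF25-75 from the blow with the largest FEV1 + FVC (full-blow FEV1 assumed at 60-70% of FVC). The overstatement is about 10% if effort scales flow and volume together, and about 6% if effort changes only the emptying rate. The highest-value rule gives 12.8% in both cases.

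**3. Change from baseline** (three blows, mono-exponential):
- Same completeness at both visits (90-100%, CV 5%): bias about 0.
- Completeness 97-100% at baseline and 90-100% later (CV 5%): a spurious rise of about 6% of the full-blow value under the highest-value rule. With the largest FEV1 + FVC blow it is about 1-4%, depending on how effort acts. If completeness improves instead, the error has the same size and the opposite sign.
- Every blow shortened, from 95-100% to 85-90% (CV 0): +13.5 points under the highest-value rule and +13.7 points with the largest-FVC blow.

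**The case against.** The strongest reply is that the rule may rarely apply. It depends on there being several measurements at a time point, and the documents do not say how many blows reach the eCRF. Spirometry must meet ATS/ERS standards, and inclusion criterion 11 requires reproducible performance, so quality control may remove badly shortened blows first. The unseen Study Manual may already fix which blow supplies FEF25-75. All of this stands and limits how far the point reaches. It does not make the rule right for FEF25-75 in the situation for which the SAP wrote it.

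The sizes are also model-dependent, and in the nearly complete case with 5% effort variation changing the rule gains almost nothing (5.9% against 5.8%). That stands too.

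A reader might infer two stronger things:

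- **That the rule always selects the least complete blow.** This is certain only if effort is identical across blows. With realistic variation it is a tendency.
- **That the rule would hide airway harm as better flow.** The documents do not support this. The bias in change is about zero when completeness is stable, and the same rule applies in both blinded arms. If dosing shortened every blow, the rise would belong to FEF25-75 itself and neither rule would remove it. Airway safety does not rest on this parameter: the bronchospasm criterion (Protocol 4.3.1), the potentially clinically significant categories (SAP 11.3) and the separate change summary (SAP 11.3.1) all use FEV1. FVC, which would fall with shortened blows, is also reported.

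**Conclusion.** The point holds as a small correction. Where several blows are recorded, the stated rule is unsuitable for one of the three parameters it covers: it leans towards shorter blows, raises observed FEF25-75 and can pair it with an FVC from another blow. The direction follows from the protocol's definition, provided flow falls as the lung empties. The sizes rest on the assumptions listed above, and the rise in change from baseline of about 6% needs completeness to become more variable after dosing.

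FEF25-75 is descriptive, with no test or threshold attached to it. The primary endpoint and the FEV1-based safety summaries do not depend on how it is selected.

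**What to change.** Replace the selection sentence in SAP 11.3 with wording such as:

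*Where more than one acceptable effort is recorded at a time point, the highest FEV1 and the highest FVC will be used. FEF25-75 will be taken from the single acceptable effort with the largest sum of FEV1 and FVC. The same rule applies at Baseline and afterwards and, for spirometry, overrides the earliest-value rule in Section 7.4.*

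The cost is a short SAP edit and a change to one derivation, best settled before unblinding. It needs blow-level FEV1 and FVC wherever several blows are entered. If only one value per time point is entered, nothing changes. The fix reduces the selection bias and ties FEF25-75 to one identified blow, but it does not correct for a session in which every blow was short.

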11.3.1. Change in FEV₁ from Baseline through End of Study

Forced Expiratory Volume in 1 second (FEV₁) (L) change from baseline and % Predicted FEV₁ change from baseline will be summarized by visit using summary statistics for continuous variables.

Percent predicted FEV₁ (%) will be calculated by implementing the Global Lungs Initiative 2012 regression equations. The predicted value of FEV₁ is a function of sex, age, height, and ethnicity and is of this form:

$$M = \exp(a_0 + a_1 \cdot \ln(\text{Height}) + a_2 \cdot \ln(\text{Age}) + a_3 \cdot \text{black} + a_4 \cdot \text{NEAsia} + a_5 \cdot \text{SEAsia} + a_6 \cdot \text{Other} + \text{Mspline})$$

M = predicted value

Exp = exponential function

ln() = natural log transformation

black = 1 if a subject is Black or African American, otherwise = 0

NEAsia = 1 if a subject is from North East Asia, otherwise = 0

SEAsia = 1 if a subject is from South East Asia, otherwise = 0

Other = 1 if subject is 'other ethnic group' or mixed ethnicity (i.e., subject is not indicated to be from North East Asia, South East Asia, or African American from eCRF page 'Demographics'), otherwise = 0

coefficients a0... a6 depend on the measurement and gender

Mspline = age and sex varying coefficients provided by Qanjer PH, Stanojevic S, Cole TF, et al.

The coefficients and Mspline values used for predicted FEV₁ calculations are provided in [Appendix 15.3](#).

Finally, % predicted = (measured/M) * 100.

This document is confidential.

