11.5. Vital Signs

Vital sign measurements will consist of blood pressure (systolic and diastolic), oxygen saturation, heart rate, respiratory rate, and body temperature. Descriptive summaries (number of subjects, mean, standard deviation, median, minimum, and maximum) of actual values and changes from baseline will be presented for each visit and time point. These summaries will be presented for the safety population and by treatment group. Vital signs will be performed at all study visits at prespecified time points per the Timing of Sample Collection and Procedures for the Treatment Period in Table 2 of the Protocol Appendix A.

Temperature will be summarized in Celsius (C) units. Fahrenheit (F) will be converted to Celsius using the following conversion:

$$\text{Temperature (in } ^\circ\text{C)} = 5/9 \text{ (Temperature [in } ^\circ\text{F]} - 32)$$

Potentially clinically significant (PCS) vital sign abnormalities will be categorized based on Table 13.3.1 and summarized by treatment group and assessment visit.

Table 13.3.1 Potentially Clinically Significant Values for Vital Signs

Vital Sign Parameter	Units	Criteria for PCS Values (Observed values)		Criteria for PCS values (Change from Baseline values)	
		High	Low	Increase	Decrease
Heart rate (sitting)	Beats/min	>120	<40	NA	NA
Systolic Blood Pressure (sitting)	mmHg	>180	<90	≥30	≥30
Diastolic Blood pressure (sitting)	mmHg	>110	<50	≥20	≥20
Oxygen Saturation (sitting)	%	NA	<92	≥5	≥5

A by-subject line plot will be provided by treatment group. Vital sign data will be listed chronologically by subject and visit for each vital sign parameter.

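### The SAP's spirometry tables do not isolate a fall in FEV1: Table 13.6.1 counts observed levels, and change is tabulated by visit although pre-dose and post-dose readings share visits

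*SAP*

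**What the plan says.** **Table 13.6.1 (SAP 11.3).** The title is "Potentially Clinically Significant Values for Forced Expiratory Volume Decrease". The only criteria columns are for observed values: nothing under High, and four Low bands of 70–99, 60–<70, 50–<60 and <50. The unit is a bare percent sign. The same section says that litres are recorded, so the percentage must be derived. The one FEV1 percentage that the SAP defines comes in 11.3.1: "Finally, % predicted = (measured/M) * 100", where M is the Global Lung Function Initiative predicted value. The table does not refer to it. Counts of flagged subjects "will be summarized by visit/timepoint and for any time post-baseline".

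**Change summaries.** Observed values and mean changes are presented "by treatment group and visit, using the Safety population" (11.3). For FEV1 in litres and in % predicted, "change from baseline will be summarized by visit using summary statistics for continuous variables" (11.3.1). By contrast, for vital signs "actual values and changes from baseline will be presented for each visit and time point" (11.5).

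**Choice among several readings.** SAP 11.3 says "If multiple measurements are to be performed at each time" and, across a page break, "point, the highest value will be used for analysis". SAP 7.4 has a general rule for repeated observations at a visit: the earliest non-missing value goes into summary tables, and the others are treated as unscheduled and generally left out of them.

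**Schedule and baseline.** Protocol Appendix A, Table 2 places spirometry before and after dosing on Days 1 and 10. SAP 7.2.1 takes the last non-missing value before the first dose as baseline.

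**The concern.** Protocol 1.3.2.2 names bronchial irritation as a potential risk of nebulised phage and lists spirometry in the Day 1 monitoring for it. Change in spirometry is also an exploratory endpoint. SAP 9.2.3 gives that endpoint no method of its own and only refers to the spirometry section (cited as 10.3, evidently 11.3). The same tables therefore serve both purposes.

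Two features work against them. A table titled as a decrease counts levels, so in a population with impaired lung function it may mostly describe how subjects entered the trial. The change tables also do not say which reading represents a visit that has both a pre-dose and a post-dose value, and one general rule in the SAP would select the pre-dose value. At stake is whether the summary tables show a post-dose fall in FEV1, which is the pattern that bronchial irritation would be expected to produce.

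**Working it through.** The plan gives no figure of its own to reproduce here. The check applies its bands and selection rules to its own schedule.

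**Inputs**
- Bands: <50, 50–<60, 60–<70, 70–99; above 99 not flagged (SAP Table 13.6.1).
- Eligibility: FEV1 at least 35% predicted (Protocol 4.1, criterion 8).
- Base of the percentage: taken as % predicted. M is assumed constant within a subject over this short study, so a relative fall in litres equals the relative fall in % predicted.
- No distribution of baseline FEV1 is assumed.

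**Step 1: no fall at all.** A subject at 40% predicted throughout is in the <50 band at every visit; one at 90% is in 70–99 at every visit. Any stable value from 35 to 99 is flagged after baseline with a decrease of zero.

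**Step 2: the fall needed to change band.** The limiting relative fall is 1 − (lower edge of band ÷ baseline).

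| Baseline, % predicted | Lower edge | Limiting fall |
|---|---|---|
| 35 to <50 | none | no fall changes the band |
| 55 | 50 | 1 − 50/55 = 9.1% |
| 65 | 60 | 1 − 60/65 = 7.7% |
| 75 | 70 | 1 − 70/75 = 6.7% |
| 85 | 70 | 1 − 70/85 = 17.6% |
| 95 | 70 | 1 − 70/95 = 26.3% |
| 99 | 70 | 1 − 70/99 = 29.3% |

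At the other extreme, 70 to 69.9 changes band with a fall of 0.1/70 = 0.14%.

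**Step 3: a 15% relative fall, as a yardstick.** The band is unchanged where x and 0.85x share a band:
- 35 to <50: always.
- 50–<60: from 50/0.85 = 58.8 to <60.
- 60–<70: nowhere, since 60/0.85 = 70.6 lies outside the band.
- 70–99: from 70/0.85 = 82.4 to 99. For example, 95 falls to 80.75 and stays in 70–99.

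**Step 4: schedule.** Matching the nine cells of the Table 2 spirometry row to its nine column headings gives five treatment-period readings:
- Day 1 pre-dose
- Day 1, one hour after the second dose
- Day 5 pre-dose
- Day 10 pre-dose
- Day 10, one hour after the first dose

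Two of the five are post-dose, and each shares its visit with a pre-dose reading.

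**Step 5: what a by-visit table would show.** As an illustration, take Day 1 pre-dose 2.00 L (the baseline under 7.2.1) and post-dose 1.70 L.
- By visit, with the 7.4 earliest value: 2.00 − 2.00 = 0.00 L.
- By time point: 1.70 − 2.00 = −0.30 L, a fall of 0.30/2.00 = 15%.

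Under the 7.4 rule the Visit 1 change is zero for every subject whose Day 1 pre-dose value is baseline, whatever happens after dosing. At Visit 3 the pre-dose change is tabulated and the post-dose change is not.

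**The case against.** The strongest reply is that the SAP's intent can be read from its text. The percentage is headed as an observed value, and only % predicted is defined, so the table may simply carry a stray word in its title. The highest-value rule is worded per time point, the flagged counts are by visit and time point, and 11.3 adopts the Table 2 timing. The 7.4 rule speaks of repeated observations and fits scheduled post-dose readings poorly; that it would make Visit 1 change identically zero argues against applying it. Any fixed banding hides some falls. Laboratory results are flagged by severity grade or normal range, without a change criterion. Nothing in the protocol demands a change-based flag for spirometry, and these summaries are descriptive.

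Much of this stands, and it limits the point. It does not remove it. Reading the percentage as % predicted is what makes a table titled as a decrease count stable subjects. The placebo comparison helps only partly: with 24 subjects per cohort at 2:1, the planned groups are 16 and 8, so a chance difference in baseline level could drive the counts. For the change tables, 11.3 and 11.3.1 say visit where 11.5 says visit and time point, and nothing disapplies 7.4.

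Three stronger inferences are tempting and are not supported:
- **The percentage means percent of baseline.** The observed-values heading and the definition in 11.3.1 point the other way, so no magnitude is built on that reading.
- **The table conflicts with Protocol 4.3.1.** That section contains a 15% FEV1 decrease, but within an individual hold-and-review rule that also requires symptoms needing intervention and persistence after a bronchodilator. A descriptive table does not contradict it. The 15% above is only a yardstick.
- **The highest-value rule masks post-dose falls.** As worded, it applies within a time point, not across a visit.

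**Conclusion.** The point holds as a modest defect in the summary tables. Table 13.6.1 does not measure what its title names: stable subjects at 35–99% predicted are counted, and a 15% fall changes nothing for the baseline ranges in Step 3. How many subjects this affects cannot be stated, because the documents give no baseline distribution.

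The change tables leave open how the two post-dose readings enter. The zero Visit 1 change and the missing Day 10 post-dose change follow only if 7.4 is applied across scheduled time points and the Day 1 pre-dose reading is available as baseline.

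A reader might infer that post-dose spirometry is lost to the report. It is not: by-subject listings, by-subject line plots and the time-point counts of flagged values all keep it. What may be missing is a summary of post-dose change by treatment group. The conclusion rests on the percentage being % predicted and on M being constant within a subject.

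**What to change.** 1. In SAP 11.3 and 11.3.1, summarise observed values and changes from baseline by visit and scheduled time point, with pre-dose and post-dose shown separately, as 11.5 already does for vital signs. State that the earliest-value rule in 7.4 does not apply across scheduled time points.
2. In Table 13.6.1, label the percentage as % predicted, or state the base if another was intended. Then either present the bands as a shift from baseline or add a tabulation of FEV1 change from baseline. Any cut-off for that tabulation is the sponsor's to choose.

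The cost is a few sentences in the SAP and minor table programming. The readings are already scheduled, so no new data are needed. Making the change before unblinding avoids settling the definitions once results by group are known.
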